#### **4. Study Procedures:**

There will be a total of five study visits required for each patient. There will be one scheduled visit for baseline evaluation and four additional visits at 2 weeks, 4 weeks, 6 weeks during treatment and 8 weeks (2 weeks post stopping the treatment). The baseline visit will involve completion of a standardized intake form, which will include pertinent demographics such as age, height, weight, education level, occupation, and comorbidities of the study patient (see Table IV). Several clinical assessments will be performed at baseline as well as at each study visit to evaluate severity of neuropathy and skin perfusion as described in the table IV.

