
Baseline & each 2- week follow-up (week 2, week 4, week 6, and week 8)
 
+ 2 day visit window for each protocol related visit starting at Week 2.
	
Peripheral Neuropathy: We will evaluate Vibration Perception Threshold (VPT) Testing to evaluate large fiber neuropathy
 
We will also use Semmes-Weinstein monofilaments, and the Modified Neuropathy Disability Score. (Armstrong and Lawrence 1998) We will assess light touch and pressure sensation at nine sites on each foot using 4, 10, 26, and 60 Semmes-Weinstein gram monofilaments. (Diamond, Mueller et al. 1989) The Modified Neuropathy Disability Score is a scored clinical examination that includes Achilles deep tendon reflex, pressure, vibration sensation and temperature sensation in both feet. (Abbott, Carrington et al. 2002; Caselli, Spallone et al. 2006).
 
Pain: Visual Analogue Scale
 
Gait test: 8 sensors will be attached to the legs and lower back using comfortable straps and will be asked to walk 20 meters on a flat surface, two times. A third 20 meter walk will be performed with an additional distractive cognitive task (counting -1). The 4th test will be fast walking. Walking performance (e.g., speed, cadence, and stability) and spatio-temporal parameters of gait (e.g., velocity, stride time, gait inter-cycle variability, double support, and gait initiation) will be measured.
 
Balance test: The BalanSens™ kinematic sensor will be attached to the legs and lower back and will be used to measure the variation of subject's center of mass measured by the Romberg protocol including double stance, semi-tandem, and full-tandem tests. Patients will be asked to stand straight, feet together, hands crossed for 30 seconds, 20 seconds, and 15 seconds respectively for double stance test, semi-tandem, and full tandem tests with eyes open and closed.

Baseline and 6 weeks follow-up
	
Activity Monitoring: Spontaneous daily physical activity will be monitored in home environment for 2 days using PAMSys™
 
Removal log: participants will be asked to note the time off, time on, and reason for removal if the PAMSys™ is removed during the 2 day collection period. Refer to Activity Monitoring Log for times of use and removal.
 
Quality of life questionnaire: SF12 will be administered.

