
For the purpose of gait analysis, subjects will be asked to walk at their habitual speed in a distance of approximately 20 meters while wearing the gait analyzer sensors (Fig 13). The system allows extracting over 30 spatio-temporal parameters of gait including stride velocity, stride length, stride time, stance, double support time, COM in medial-lateral and anterior-posterior, and gait initiation(Najafi, Helbostad et al. 2009; Najafi, Miller et al. 2010). We assumed that the performance of gait and dynamic balance will be improved in the intervention group after treatment compared to baseline and compared to sham group (Hypothesis 2). Additionally, we anticipate that the inter-cycle gait variability and gait initiation will be improved after treatment in the active group compared to

[figure not shown]
baseline and compared to sham group.

**Specific Aim 2:** Our second aim is to compare changes in skin perfusion in patients treated with Electrical Stimulation (ESTIM) compared to sham therapy. We anticipate that electrical Stimulation will improve dorsal and plantar perfusion compared to the control group and compared to baseline (Hypothesis 3). As described in the clinical assessment (Table IV), we will assess perfusion of the macro-circulation with arterial Doppler studies and micro-circulation with Skin Perfusion Pressure measurements and transcutaneous oxygen measurements.

**Specific Aim 3:** Our last aim us to evaluate changes in quality of life in high risk diabetes that receive Electrical Stimulation compared to sham therapy. Our hypotheses and methods of assessment described in the following:

Hypothesis 4: We assume that plantar electrical stimulation will improve subject quality of life in the intervention group. Quality of life will be assessed using SF-12 questionnaire (Melville, Lari et al. 2003) at the baseline visit and at week 6.

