### **14. Biostatistics:**

**Power & Sample Size Estimation:** The sample size for the study was designed to achieve 85% power when comparing the change in the actively treated group to the change in the sham treated group, using assumed rates of 50% and 10% improvement, respectively. A two-sided test of results in evaluable subjects (qualified for analyses of efficacy on vibration perception threshold and on structured S-W monofilament testing) will provide the specified power at a 5% significance level. Sample size calculations resulted in a requirement for a total of twenty-seven (27) subjects in each group. The sample size was also estimated using our pilot data in which we explored the benefit of plantar stimulation for improving balance (Study 5). At baseline, the area of sway for center of mass (COM) was  $5.23 \pm 2.81 \text{ cm}^2$  and  $5.41 \pm 1.14 \text{ cm}^2$  respectively for the sham and intervention groups. After week two of treatment, the area of COM sway was  $4.94 \pm 3.42 \text{ cm}^2$  for the sham and  $3.49 \pm 1.25 \text{ cm}^2$  for the intervention group. Using the same criteria explained above, to observe a significant improvement in the intervention group receiving active stimulation compared to sham group (with nonfunctional stimulator), twenty seven subjects per group is required. Assuming 10% drop out, therefore, 40 subjects per group (a total of 80 subjects) should be enough for the purpose of this study.

No suitable alternative treatments exist for patients with loss of protective sensation due to diabetic peripheral neuropathy, so a statistically detected difference in improvement between groups may be considered a clinically meaningful result. However, the study was designed to detect a sufficiently large difference to account for an anticipated “placebo effect” in the sham treated group.

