### **Analysis Plan:**

P-values of 0.05 or less will be considered statistically significant based on a two-sided test unless otherwise noted. All variables will be tabulated descriptively at each scheduled time point. For each continuous variable, the analyses will include the mean, standard deviation, minimum and maximum. For each categorical variable, the summary will include frequencies and percentages. Each variable will be analyzed using all available data. Baseline variables will be summarized using descriptive statistics. Between-group differences for primary and secondary endpoints will be explored at the time of the last treatment visit (weeks 12) and every two weeks of treatment.

Additionally, the retention of potential benefit will be assessed at the time of follow-up visit following the completion of treatment (two weeks post termination of treatment). The frequency of subjects

with adverse events (AEs) will be tabulated. AEs will also be tabulated by severity and, when appropriate, by relationship to study treatment. The difference in the occurrence of adverse events between the study groups will be compared descriptively.

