To determine whether gait, balance, and physical activity variables change significantly across different study visit epochs, within-subject analyses of variance (ANOVA's) will be employed. We assume that plantar electrical stimulation is helpful to improve subjects gait, balance, and physical activity. Then sensor-derived movement variables should change substantially from baseline to the end of the study for the active group with no significant change in placebo group. For example, the range of motion of COM and RCI values should be reduced and gait velocity should be increased. Next, for all continuous variables, pretreatment scores will be regressed on post-treatment scores to form residualized change scores (e.g. VPT, monofilament test, pain intensity, A1C, etc). Correlations will then be generated among these scores to determine whether changes in sensor-derived movement factors are related appropriately with increases in (clinically assessed) functional capacities and self-report measures of activities, mood, socializing, etc. ANOVA test will be used to examine significant difference between intervention and sham group at baseline for age and BMI as well as the indicated outcomes (e.g. gait, balance, VPT, ABI,. Etc). We assumed there is no significant difference between sham and intervention group at baseline for the indicated variables. The same test will be repeated for the week 12. We assumed that the outcomes of study will be improved in the intervention group compared to the sham group. Paired- sample t-test will be used to examine the retention of the electrical stimulation therapy at two weeks post stopping the therapy compared to week-12. We assumed the benefit of the electrical stimulation therapy will be retained at least for two weeks. Additional analyses will examine the degree to which early-treatment changes in cognitive variables and functional capacity variables (representing functional restoration processes) predict late-treatment changes in moving ability post plantar electrical stimulation therapy. Such analyses will also allows to elucidate the relative contributions fear of falling (assessed using FES score); and/or and range of motion (assessed using body worn sensors) made to bringing about clinically meaningful changes in gait balance control. Moderator effects will also be examined for exploratory purposes. Using gender as an example, mixed design ANOVA's will be conducted to determine whether gait and balance factors change over the course of treatment at different rates or with different patterns for men and women as well as for patients with high or low severity of neuropathy and peripheral vascular disease. We assume those who have higher peripheral vascular problem will receive maximum benefit from electrical stimulation. Additional analyses will test whether changes in gait and balance variables predict changes in clinically important outcome factors (e.g., fear of falling (FES) , quality of life (SF12), adverse events, foot ulcer, etc) depending on gender.

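### The only named active-versus-sham efficacy test ignores baseline (65% power for COM sway on the pilot figures), and the residualized-change regression is written the wrong way round

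*Combined protocol and SAP*

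**What the plan says.** Under Power & Sample Size Estimation in Section 14, the 85% power is stated to apply "when comparing the change in the actively treated group to the change in the sham treated group".

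The Analysis Plan in the same section then says: "Between-group differences for primary and secondary endpoints will be explored at the time of the last treatment visit". It names no model for this. Further down, "ANOVA test will be used to examine significant difference between intervention and sham group at baseline", and for the efficacy comparison "The same test will be repeated for the week 12". Neither a baseline covariate nor a change score is mentioned.

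The other named methods do not compare active with sham:
- Within-subject ANOVA looks at change across visits.
- The paired t-test addresses retention two weeks after stopping.
- Mixed-design ANOVA is exploratory, for moderators such as gender and severity.
- Residualized scores feed correlations only. For these, "pretreatment scores will be regressed on post-treatment scores to form residualized change scores".

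On timing, Section 4 plans a baseline visit and "four additional visits at 2 weeks, 4 weeks, 6 weeks during treatment and 8 weeks (2 weeks post stopping the treatment"). Table IV likewise lists "week 2, week 4, week 6, and week 8". Hypothesis 4 under Specific Aim 3 plans the SF-12 "at the baseline visit and at week 6".

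**The concern.** Three things need attention.

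1. **Precision.** The trial is sized on change, but the named test compares final values alone. For any continuous outcome whose baseline predicts its later value, leaving baseline out widens the confidence interval for no gain. Balance is the Aim 1 outcome and one of the two sizing arguments, so the loss matters most there.

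2. **Direction of the residual regression.** A residualized change score is the part of the post-treatment value that baseline does not predict. Regressing pretreatment on post-treatment scores instead gives the part of *baseline* that the post-treatment value does not predict. Correlating two such residuals can produce an association between changes that comes only from correlated baselines.

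3. **Time point.** The test is placed at week 12, which is not in the visit schedule, so it cannot be run as written.

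**Working it through.** **Inputs (Section 14, Power & Sample Size Estimation).** Two-sided 5%; 85% power; rates of 50% and 10%; 40 per arm less 10% drop-out = 36 evaluable. Pilot COM sway in cm²: baseline 5.23 (SD 2.81) sham and 5.41 (SD 1.14) active; week 2 4.94 (SD 3.42) sham and 3.49 (SD 1.25) active. The baseline-to-post correlation r is not given, so every value of r below is an assumption.

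**The plan's own figure.** For 50% v 10%, n = [1.960√(2×0.3×0.7) + 1.036√(0.25+0.09)]²/0.4² = 22 per arm. With continuity correction this becomes 26.7, rounded up to 27, which matches the protocol. At 36 per arm, Fisher's exact test has about 96% power, so this calculation is not in question. The second 27, for COM sway, does not follow from the printed figures alone. Week-2 values give 57 per arm (normal approximation) or 58 (noncentral t). A change-score comparison gives 27 only if r is about 0.66.

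**Final values only.** Difference = 4.94 − 3.49 = 1.45. Pooled SD = √((3.42² + 1.25²)/2) = 2.575. Noncentrality = 1.45/(2.575√(2/36)) = 2.39 on 70 df, giving power 65.4%. The 95% CI half-width is 1.21.

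**Adjusted for baseline (ANCOVA).** Residual SD = 2.575√(1 − r²), 69 df, same difference of 1.45:

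| Assumed r | Residual SD | Power | CI half-width | n per arm for 85% |
|---|---|---|---|---|
| none (ANOVA) | 2.575 | 65% | 1.21 | 58 |
| 0.1 | 2.562 | 66% | 1.20 | 58 |
| 0.3 | 2.456 | 70% (69.5%) | 1.16 | 53 |
| 0.5 | 2.230 | 78% | 1.05 | 44 |
| 0.65 | 1.957 | 87% | 0.92 | 34 |
| 0.7 | 1.839 | 91% | 0.87 | 30 |

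Power equals 85% at r = 0.618. A simulation with the unequal pilot SDs (20,000 replicates) gave ANCOVA power of 65%, 69%, 77%, 87% and 90% at these five r, with type I error of 5.1% to 5.5%.

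**If change v change is intended.** The pilot changes are 5.41 − 3.49 = 1.92 and 5.23 − 4.94 = 0.29, a difference of 1.63. The change variance in each arm is SD_pre² + SD_post² − 2r·SD_pre·SD_post. The pooled change SD is then 3.182, 2.814, 2.389, 2.014 and 1.872 at the five r, and power is 57%, 68%, 81%, 92% and 95%. An ANCOVA credited with the same baseline difference of 0.18 gives 67%, 73%, 83%, 93% and 95%. It is no worse than the change score at any of these r, and clearly better at low r.

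**Reversed residuals.** With standardized scores, regressing baseline on post leaves a residual that correlates √(1 − r²) with baseline: 0.95, 0.87 and 0.71 at r = 0.3, 0.5 and 0.7. Take two outcomes whose baselines correlate c and whose changes are otherwise unrelated. Their reversed residuals then correlate c(1 − r²); for c = 0.5 and r = 0.3 that is 0.5 × 0.91 = 0.455. Simulated rates of a significant correlation (n = 72, 4,000 replicates):

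| Assumed c | r = 0.3 | r = 0.5 | r = 0.7 |
|---|---|---|---|
| 0 | 5% | 5% | 5–6% |
| 0.2 | 31% | 24% | 14% |
| 0.5 | 98% | 90% | 59% |

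In the correct direction the rate stays near 5% throughout.

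**Time point.** The Analysis Plan tests at week 12 and assesses retention two weeks later. Section 4 and Table IV end treatment visits at week 6 and place the post-treatment visit at week 8. Section 1 describes twelve weeks of treatment and monthly balance testing, and the fall log in Table IV refers to a four-week study period.

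**The case against.** The strongest reply is that nothing here is invalid. A final-value ANOVA in a randomized trial holds its 5% level, so ANCOVA is an efficiency gain, and its size depends on an unreported correlation: under one percentage point at r = 0.1, about 26 points at r = 0.7. The 65% itself rests on a week-2 difference from thirteen subjects using foot baths (Study 5 in Section 2). If they split 6 and 7 (arm sizes are not given), the Welch 95% interval for the 1.45 difference runs from about −1.8 to 4.7, or −2.1 to 5.0, so true power could be almost anything. The 50% v 10% sizing is unaffected. The sizing text speaks of change, and the sentence on between-group differences names no model, so an analysis using baseline is not excluded. The reversed regression may be a slip of wording, its residual tracks baseline less closely as r rises, and it does not touch the treatment test.

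All of that stands as a limit on size. It does not remove the point. An analyst following the text would run the unadjusted test and the reversed regression. The alternative is not less powerful at any r examined, and leaving the model open is itself a reason to state one.

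**Conclusion.** The concern holds and should be fixed. It is a loss of precision in the treatment comparison, not a bias. For COM sway on the pilot figures with 36 per arm, the named test has 65% power. Baseline adjustment gives 66% to 91% for assumed r of 0.1 to 0.7 and reaches 85% only from about 0.62. These figures assume that a small week-2 pilot with a different device carries over to the end of treatment here, so they show the direction and possible size of the gain and do not forecast this trial's power. The regression is reversed as written. This affects only the planned correlations among changes, and how badly depends on how strongly the baselines correlate. The week-12 analysis cannot be run on the visit schedule as it stands.

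**What to change.** In Section 14:

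- State that efficacy for each continuous outcome is the active-minus-sham difference with 95% CI at the last on-treatment visit, from an ANCOVA adjusted for the baseline value of that outcome. For outcomes measured at every visit, a mixed model with baseline, treatment, visit and treatment-by-visit is an alternative. The SF-12, measured at baseline and once afterwards, needs the ANCOVA.
- Present within-arm changes descriptively; a change in one arm and none in the other is not a between-arm comparison.
- Add the same between-arm contrast at the post-treatment visit beside the planned paired comparison, and do not read a non-significant paired test as evidence of retention.
- Reword the residual step so that post-treatment scores are regressed on pretreatment scores.
- Reconcile the analysis time point with Section 1, Section 4, Table IV and Hypothesis 4. Which schedule is right is for the sponsor to settle.

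The cost is revised wording and one degree of freedom per ANCOVA. Standard software suffices, and no new data or visits are needed.

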
Other assessment
	
Fall log: participant will receive a log and agree to call the study overseer in the event of a fall during the 4 weeks study period.
 
Other patient information: if it was available patients record including medical history, neurological exam results, and physical examination may be gathered from patient record after authorization of the subject (see form T504a). In addition, subject photograph or video during experiment may be taken after subject's authorization.

Baseline & each 2- week follow-up	
Vascular Assessment: We will assess perfusion of the macro-circulation with arterial Doppler studies and micro-circulation with Skin Perfusion Pressure measurements and transcutaneous oxygen measurements. Ankle Brachial Index (ABI), Toe Pressures and Waveforms (pulse volume recordings) will be measured on both extremities. If the ankle is too painful to perform a Doppler examination, we will get Doppler measurements once the patient is in the operating room and under anesthesia. ABI's have been reported to be reliable measurements for diagnosing peripheral vascular disease. ABI's have a 95% sensitivity in detecting angiographically positive disease in an ABI of less than 0.9. Non-compressible foot vessels will be defined as ABI's <math>>1.30</math>. Peripheral arterial occlusive disease will be defined as an ABI <math><0.90</math>. Monckeberg's medial calcific sclerosis or calcification of the media of the arteries can limit the effectiveness of using ABI's in persons with diabetes. Therefore, we will use the SensiLase system (Väسامد) to measure Skin Perfusion Pressure (SPP) in mmHg and records PVR waveforms with its laser Doppler sensor and computer-automated cuff. This technique has high sensitivity and high positive and negative predictive value to predict amputation.(Castronuovo, Adera et al. 1997; Yamada, Ohta et al. 2008) In addition we will measure transcutaneous oxygen measurements at 2 sites on the foot and two sites on the lower leg during the course of therapy.

-----------------------------------	--

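### The exploratory moderator analysis splits graded baseline severity into high and low groups at an unstated cut, which costs information if the effect is roughly linear and leaves the result open to the choice of cut

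*Combined protocol and SAP*

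**What the plan says.** Section 14, Analysis Plan, introduces this work as exploratory: "Moderator effects will also be examined for exploratory purposes". Taking gender as the example, it proposes mixed-design ANOVAs "to determine whether gait and balance factors change over the course of treatment at different rates or with different patterns" for men and women, and likewise for "patients with high or low severity of neuropathy and peripheral vascular disease". It gives no cut for either severity factor, no measure to define it, and no analysis that keeps severity graded. Treatment arm is not named as a factor in these ANOVAs.

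The same paragraph then makes a directional prediction, for vascular disease only: "We assume those who have higher peripheral vascular problem will receive maximum benefit from electrical stimulation".

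Table IV supplies graded baseline measures for both constructs:

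- **Neuropathy:** "We will evaluate Vibration Perception Threshold (VPT) Testing to evaluate large fiber neuropathy", several monofilament weights, and a composite score ("The Modified Neuropathy Disability Score is a scored clinical examination").
- **Vascular disease:** "Ankle Brachial Index (ABI), Toe Pressures and Waveforms (pulse volume recordings) will be measured on both extremities", a laser Doppler system "to measure Skin Perfusion Pressure (SPP) in mmHg", and transcutaneous oxygen at two foot and two lower-leg sites.

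Two vascular cuts appear elsewhere. Table IV gives ABI below 0.90 as a diagnostic definition, and itself warns that arterial calcification limits ABI in diabetes. Background Study 4 uses a transcutaneous oxygen value of 40 mm Hg. Neither is linked to the moderator analysis.

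**The concern.** A two-level factor treats a patient just above the cut like the most severe patient in the trial, and unlike a patient just below it. If benefit rises steadily with severity, that discards information already collected. With at most 80 patients, tests of who benefits are weak to begin with.

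The second problem does not depend on the shape of the effect. With neither the measure nor the cut stated, the line could be drawn after the data are seen, and the moderator result could depend on where it falls. Section 1 says data from this study will be used to plan a later trial in high-risk patients, so a finding about who benefits may be carried forward.

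**Working it through.** **The plan's own figure.** None exists for moderators. The 27 per group in Section 14 is reproduced by the continuity-corrected two-proportion formula (50% v 10%, 85% power, two-sided 5%), but it concerns the main comparison and has no bearing here.

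**Step 1: information lost by splitting.** For a linear moderator effect, a high/low indicator I keeps a fraction corr(X, I)² of the information in severity X.

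- Normal X, fraction q below cut c: retained = φ(c)² / [q(1 − q)]. At the median: 0.3989² / 0.25 = 0.637 = 2/π, a loss of 36%.
- Uniform X: retained = 3q(1 − q). At the median: 0.75, a loss of 25%.

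The documents give no distribution for either measure, so a range is needed:

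| Severity measure and cut | Loss |
|---|---|
| Uniform or bimodal, median | 25% |
| Normal truncated at ±1 SD, median | 27% |
| Beta(2,2), median | 30% |
| Normal, median | 36% |
| Normal, 30/70 | 42% |
| Normal, 20/80 | 51% |
| t with 5 df, median | 46% |
| Lognormal (0.5), median | 48% |
| Exponential, median | 52% |

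An uneven cut usually loses more than the median. The exception is a right-skewed measure cut further into its tail: exponential severity cut at the 70th percentile loses 38%.

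In patient numbers, 40 per arm less the plan's 10% dropout is 36 per arm, 72 in all. A median split makes 72 patients act like 72 × 0.637 = 46 (normal) or 72 × 0.75 = 54 (uniform).

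**Step 2: illustrative power for an arm-by-severity interaction.** Assumptions: 72 patients, residual SD 1, standard normal severity, two-sided 5%.

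One reference slope comes from the week-2 sway data in Section 14. The difference is 4.94 − 3.49 = 1.45. The pooled SD is √[(3.42² + 1.25²)/2] = 2.575. The ratio is 1.45/2.575 = 0.563. Setting the slope per SD of severity equal to this whole mean effect is a choice, not a figure from the plan.

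Analytic check: SE of the interaction = 2/√72 = 0.236, so the non-centrality is 0.563/0.236 = 2.39. A median split multiplies it by √(2/π) = 0.798, giving 1.90.

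Simulation (6,000 trials per setting, t-test of the interaction):

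| Slope (SD per SD) | Continuous | Median split | Fall |
|---|---|---|---|
| 0.4 | 37% | 25% | 12 points |
| 0.563 | 62% | 44% | 18 points |
| 0.7 | 80% | 59% | 21 points |

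With uniform severity and slope 0.563, power falls from 63% to 50%. At slope 0.2 the normal approximation gives about 14% v 10%, and neither analysis is informative.

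**Step 3: what if the effect is a threshold?** Step of 2 × 0.563 = 1.13 SD, 36 per arm:

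| True threshold | Cut used | Split | Continuous |
|---|---|---|---|
| Median | Exactly at threshold | 65% | 44% |
| Median | Sample median | 55% | 44% |
| Median | 70/30 | 32% | 44% |
| 70th percentile | Sample median | 27% | 35% |

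The split wins when its cut is at or very near the true threshold. It loses when the cut is misplaced.

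**The case against.** The strongest objection is that the documents' only evidence on who responds fits a threshold at least as well as a line. Study 4 reports a significant rise in oxygenation below 40 mm Hg (p < .040) and no significant rise above it (p = .280). Eleven of its 19 subjects (57.9%) were impaired, so that cut would fall near the median. Under such a threshold the split gains 21 points (65% v 44%), more than it loses at slope 0.563. This stands as a limit. It does not rescue the text, because the Analysis Plan adopts no such cut, Study 4 measured oxygenation and not balance, and Step 3 shows that a misplaced cut does worse than the continuous test.

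Other points stand as limits on size:

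- The analysis is exploratory, with no power claimed for it.
- The power figures describe an arm-by-severity test, which the prediction about benefit calls for but the Analysis Plan does not name.
- The 0.563 comes from week 2 in a 13-patient subsample treated with a different device (Study 5), with very unequal SDs.

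A reader might infer that at least a third of the information is always lost. The documents do not support that. Flat or range-restricted severity split at the median loses 25 to 30%, and restriction is plausible: Section 7 excludes some clinically significant vascular disorders, and Section 3 expects mostly moderate to severe neuropathy.

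A reader might also infer that the plan predicts a graded response for both constructs. The prediction covers vascular severity only, and its wording could describe a two-group contrast.

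**Conclusion.** The point holds as a modest improvement to an exploratory analysis. The plan splits graded baseline severity at an unstated cut. Under a roughly linear effect, a median split costs about a quarter to a half of the information (25% to 52% across the shapes tried, 36% for a normal measure). The open cut is a weakness whatever the shape.

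The fall of 12 to 21 points in power rests on 36 per arm, normal severity and assumed slopes of 0.4 to 0.7. It is illustrative, not a property of the plan. It would be wrong to infer that the continuous test is always better, since a threshold exactly at the cut reverses the ranking. For neuropathy the case rests on information loss and the open cut alone, because the plan makes no directional prediction there. Nothing here touches the main between-group comparison.

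**What to change.** In Section 14, Analysis Plan, replace the high/low severity wording with the following:

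1. Name one baseline measure per construct, without alternatives, and state its limb or site rule. For example, use VPT for neuropathy and SPP for perfusion, each with a stated rule for combining or choosing between feet. Offering alternatives would restore the freedom of choice the change is meant to remove.
2. Test the arm-by-severity interaction in a regression or mixed model with severity continuous, and include a linearity check. This also names treatment arm in the moderator model.
3. Report the treatment effect with 95% CI at the 25th, 50th and 75th percentiles of severity.
4. Keep any high/low comparison as supportive only, with measure, site and cut fixed before unblinding. A cut already in the documents could serve, such as transcutaneous oxygen 40 mm Hg from Study 4. It would need a site rule, because Table IV has four sites.
5. Keep gender as a two-level factor and keep the analysis labelled exploratory.

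The cost is a few sentences, with no new data, visits or patients. The downside is that the main moderator test assumes a roughly linear relation and loses power if the true effect is a threshold at the cut. The linearity check and the supportive pre-fixed cut are there to cover that case.
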